## AUTO Study Protocol: Version Date: 12/22/21 PI: [name], MPH COMIRB No: 19-0059 **Table 3. Key study measures**. Shown in relation to measurement point (pre- or post- DDA or website

Participant, and analytic plan. • = about self,  $\circ$  = as surrogate about older driver

		[name]/friends			Analytic Plan				
Domaiı	n and Key Measures	En	roll	F/u	Enr	oll	F/u			
		Pref	Post		Pre	Post			Hypoth.	Scoring
Immediate outcome										
Decision Conflict	Decisional Conflict Scale (DCS)	•	•	•	٠	•	•	1° Outcome	1a, 2a, 2b, 2c	Score <25
Knowledge	Knowledge questionnaire	•	•	•		•	•	2° Outcome	1a	Descriptive (cat.)
Values concordance	DCS Values Clarity subscale	٠	٠	•	٠	٠	٠	2° Outcome	1a	Descriptive (cat.)
Self-efficacy	Decision Self-Efficacy scale	•	•	•		•	•	2° Outcome	1a	Descriptive (contin.)
Longitudinal outcome										
Depression	PROMIS depression	٠		٠				2°	1b	T-score >50
								Covariate	1c	Descriptive (contin.)
Decision regret	Ottawa Decision Regret Scale			•			•	2° Outcome	1b	Descriptive (contin.)
Life space	Life-Space Assessment	٠		•			0	2° Outcome	1b	Descriptive (contin.)
Driving behaviors	Amount; reduction or cessation	•		•			0	2° Outcome	1c	Descriptive (cat.)
Subgroups										
Cognitive	5 minute MoCA			٠			•	Eligibility		Score ≥21
screening								Covariate	•	
Cognitive function	BTACT, OTMT	•						Stratify	2a	Normal vs. impaired
Insight	Beck Cognitive Insight Scale	٠		٠				Stratify	2a	R-C index ≥3
Decisional capacity	SPACED	•		•				Stratify	2b	# correct answers
Attitudes about	ARMT	٠		٠				Stratify	2c	Mean score ≥3.57
anning								Covariate	1c	_0.07

	Drivers	Family/fri	Analytic Plan				
Domaii	n and Key Measures	Enroll F	/u Enroll	F/u			
		PrePost	Pre Post			Hypoth.	Scoring
Other covariates							
Demographics	E.g., age, gender, race/ethnicity, marital/home status, education, income, urban/rural	•	• •	•	Covariate	all	Descriptive (cat.)
Physical health	Medical history, Activities of Daily Living, PROMIS global health	•	•	•	Covariate	all	Descriptive (cat.)
Mental health	PROMIS Emotional Support, Social Isolation; Perceived Stress Scale	•	•		Covariate	1b, 1c	Descriptive (cat.)
Personality	TIPI	•			Covariate	1c, 2c	Descriptive. (cat.)
Driving behaviors	Crashes, self-driving technologies	•	•	0	Covariate	1c	Descriptive (cat.)
Driving resources	Alternative transportation, support	•	••	• 0	Covariate	1c	Descriptive (cat.)
Driving education	Use of websites, courses, or other material driving or cessation	•	• •	•	Covariate	1c	Descriptive (cat.)

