Analysis for Aim 1: Analyses will be performed according to the principle of intention-to-treat. including all randomized drivers. Unless otherwise specified, hypothesis tests will be two-sided with alpha=.05, with 95% confidence intervals or p values reported. All canalyses will be performed using SAS/STAT® software. First, descriptive statistics will be computed for baseline patient characteristics, initially testing for differences between control and intervention groups (including for key covariates, Table 3.3). We will assess site effects by comparing demographic variables across the sites, using ANOVA for continuous measures and chi-square tests of proportions for categorical measures. If no statistically significant differences exist among sites. we will ignore site and formally test the differences in proportions or means as described below. If there are significant differences among sites, then (assuming enough events) we will use separate bivariate logistic regression models for each aim described below, with a fixed effect for site and with treatment arm as the main predictor. For longitudinal analyses, we will conduct logistic regression with unstructured correlation of generalized estimating equations (GEE) to account for the repeated observations for each participant. Statistical significance will be evaluated at one-sided p<.05 level. Analyses of the DDA's longitudinal effects may be vulnerable to bias, as control arm participants may be exposed to intervention arm messages through exposure to available materials or courses related to driving safety or cessation (e.g., websites, physician counseling, AARP courses). We will assess exposure to other sources of information through structured questions. To mitigate the impact of this potential bias, we will adjust measurements of contamination as applicable. In all analyses, validation of distributional and parameterization assumptions will be checked and data transformations (e.g. logtransformations) or alternative methods will be implemented as appropriate.

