Aim 1a. Test the DDA's effect on immediate decision quality (measured by the Decisional Conflict Scale). Hypothesis 1a: More DDA participants will have high-quality (DCS<25) scores, compared to control, immediately after the intervention. Our primary outcome measure will be the proportion of participants with DCS score <25. We will perform multiple logistic regression to test the DDA's effect on decision quality. We are also interested in jointly modeling the proportion of family members with DCS score <25, so a bivariate logistic regression model will be used for analysis to allow assessment of marginal effects of the intervention on patients and family members, as well as their concordance/discordance in decision quality. In the small pilot trial of Australian drivers with dementia, mean DCS score scores decreased from 22.5 to 7.5 (out of 100) after the DA; should we find that DCS score distributions do not allow dichotomization based on the cut-point of 25, we will instead compare means between the groups. Missing data for the primary measure should be minimal, given that this will be obtained at enrollment. Additional analyses will include examining components of decision quality to identify changes in

AUTO Study Protocol: Version Date: 12/22/21 PI: [name], MPH COMIRB No: 19-0059 measures like knowledge, values-concordance, or self-efficacy, as they may shed light on the mechanisms underlying decision-making about driving.

Family member data: In addition to the analysis under 1a, we will examine the degree of concordance (or discordance) within driver-family dyads on various measures, including current versus desired level of family involvement in driving retirement process (part of the driving questionnaire). To evaluate agreement we will look at the kappa coefficients at baseline and at follow-up points, as well as apply this class of repeated-measure concordance correlation coefficients. For longitudinal data, we will examine changes across the other time points (6, 12, 18, 24 months) using GEE after adjusting covariates.

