Aim 1b. Test the DDA's longitudinal effect on psychosocial outcomes at 12 and 24 months. Hypothesis 1b: Participants in the DDA group will have reduced prevalence of depressive symptoms and of decision regret but maintained life space, at 12 and 24 months after enrollment, compared to control participants. We will use descriptive statistics, including proportions with 95% CIs or medians and interquartile ranges, for comparison between treatment groups. We will utilize GEE with a linear link, and a linear mixed model (LMM) with a random intercept, fixed effects and a linear link for each outcome. We will adjust for baseline characteristics (gender, age, education, etc.), driving behaviors and other variables. We will perform sensitivity analyses to examine the missing assumption under maximum likelihood.

Aim 1c. Test the DDA's longitudinal effect on driving behaviors at 12 and 24 months. Exploratory: The DDA does not provide specific recommendations as to whether the participant should stop driving or not. We will compare the proportion of participants who change their reported driving behaviors (reduce driving or cease altogether) over the follow-up period to examine whether the DDA appears to affect them. We will apply GEE with a logistic link, and a generalized LMM (GLMM) with a random intercept and a logistic link for each outcome. Also, we will adjust demographic variables and appropriate variables.

Secondary analyses: Secondary analyses by gender will be conducted, as we hypothesize there will be differences in behavior and outcomes based on gender, and the belief that the responses to DDA intervention may be heterogeneous between men and women. Aim 1a-1c will be considered gender analyses using logistic regression and GLMM. We will also examine the degree of concordance (or discordance) within driver-family dyads on various measures, including DCS and current versus desired level of family involvement in driving retirement process (part of the driving questionnaire). For longitudinal data, we will examine changes across time points (follow-up at 6, 12, 18, 24 months) and correlation between older driver and family member report.

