## Study Design and Research Method

We will use a multi-site, two-armed randomized controlled trial of older drivers (n=300; ≥70 years) from clinical settings, and one family member each (n=up to 300), with longitudinal follow-up. Our goals are to test how much the DDA improves outcomes and identify who benefits most from the DDA. Our evaluation of the DDA's efficacy (Aim 1) and its relative effect in subgroups (Aim 2) corresponds to Stage II in the NIH Stage Model for Behavioral Intervention Development. Our findings from Aims 1 & 2 could identify necessary refinements (Stage I) and inform future efficacy, effectiveness or implementation trials.

**Sites:** For this multi-site trial, we plan to include clinics associated with three sites to provide geographic diversity, along with access to populations with racial and ethnic variability. We request that COMRIB serve as the single IRB for this research study, with other IRBs ceding oversight.

- **University of Colorado Health:** Participants will be recruited primarily from three clinics associated with University of Colorado Health.
  - UCHealth Senior's Clinic Aurora, CO
  - o UCHealth Internal Medicine Anschutz clinic Aurora, CO
  - UCHealth Internal Medicine Lowry clinic Denver, CO
- University of California-San Diego: Participants will be recruited primarily from five clinics and four practices associated with University of California San Diego
  - UCSD The Shiley Eye Clinic San Diego, CA
  - UCSD Neurological Institute San Diego, CA
  - UCSD Memory Disorders Clinic San Diego, CA
  - UCSD Senior Medicine Clinic San Diego, CA
  - Memory Aging and Resiliency Clinic San Diego, CA
  - UCSD Internal Medicine Practice San Diego, CA (four practices)
- Indiana University: Participants will be recruited primarily from 29 primary care clinics associated with the Indiana University School of Medicine.
  - Indiana Health Indianapolis, IN (20 clinics)
  - Eskenazi Health Indianapolis, IN (9 clinics)
    - Eskenazi Health is not a part of Indiana University and will not be actively engaged in research. They will be participating as a recruitment site only.

**Recruitment:** We will follow methods used successfully in the LongROAD cohort study. Research assistants (RAs) at each site will identify potentially-eligible older drivers by screening the electronic health records of clinic patients to identify patients aged  $\geq$ 70 years with at least one relevant medical diagnosis.

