**Randomization**: At each site, enrolled drivers (with their family members) will be randomly assigned in equal numbers to the DDA or control arm (Figure 4). To reduce bias and aim for balance among arms, we will randomize patients in blocks with randomly varied block sizes of 4 and 6. While RAs delivering the intervention to patients cannot be blinded to treatment, we will conceal allocation using a centralized, computer-generated list that RAs will access only after enrollment. Other study staff, including a different RA (whenever possible) doing follow-up calls, will be blinded to study arm.

**Baseline Measurements & Intervention**: The driver and family member will be randomized to the same arm but will complete all study measures and interventions separately from each other. For each participant (including those enrolled in person as well as those enrolled remotely by phone), the RA will use a study tablet or laptop to administer the introductory questionnaire (Figure 4, Table 3). In the intervention arm, participants will then complete the web-based DDA; control group participants will be directed to the NIA "Older Drivers" website. After completing the DDA or website review, all participants in both arms will answer questions about their knowledge, values, and plans related to driving cessation (Table 3). For family members, questions will generally be about the older driver, though there will be specific questions concerning their relationship, frequency of contact, and possible co-dependence for transportation. Whenever possible, participants will receive a printed handout of either their DDA results or the NIA webpage (for those enrolled in person) or will receive instruction from the RA about how to save an electronic copy of the DDA results or the NIA webpage (for those enrolled in person) or the NIA webpage (for those enrolled remotely by phone).

**Identifying driving risk**: At the request of the DSMB, the study team will use American Academy of Neurology (AAN) guidelines to identify drivers who are at moderate risk for being unsafe to drive (https://www.aan.com/PressRoom/home/GetDigitalAsset/8471). Per AAN

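### Site is the randomisation stratum but is dropped from the analysis unless demographics differ across sites; fit it always. The cost of dropping it is a slightly conservative Aim 1a test, not false positives.

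*Combined protocol and SAP*

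**What the plan says.** Under Study Design and Research Method, Randomization: "At each site, enrolled drivers (with their family members) will be randomly assigned in equal numbers to the DDA or control arm". Allocation uses permuted blocks of 4 and 6, and the Sites paragraph names three sites.

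Under Analysis for Aim 1: "We will assess site effects by comparing demographic variables across the sites, using ANOVA". Categorical variables get chi-square tests instead. If nothing is significant, "we will ignore site and formally test the differences in proportions or means as described below". Otherwise: "If there are significant differences among sites, then (assuming enough events) we will use separate bivariate logistic regression models for each aim described below". Those models carry site as a fixed effect. How many events are enough is not stated.

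No other paragraph makes site a fixed part of the model:
- Aim 1a: "We will perform multiple logistic regression to test the DDA's effect on decision quality". Site is not named.
- Table 3 lists demographics as covariates for all hypotheses ("E.g., age, gender, race/ethnicity, marital/home status, education, income, urban/rural") but not site.
- Aim 1b: "We will adjust for baseline characteristics (gender, age, education, etc.), driving behaviors and other variables". This list is open and neither names nor excludes site.
- Analysis for Aim 2 repeats the demographic and site check, then calls the main interaction test unadjusted and lists only arm, subgroup and their interaction.

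**The concern.** An analysis should normally include the factor that restricted the randomisation. Here its inclusion depends on significance tests of other variables. Sites can be alike in age, gender and education and still differ in DCS, for example because one site recruits from eye, neurology and memory clinics and another from primary care clinics.

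When arms are balanced within a prognostic stratum and the stratum is ignored, the usual standard error is too large for the design. The test is then conservative and loses power. Also at stake is having one primary model fixed in advance, rather than one chosen by a baseline significance test.

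**Working it through.** **The plan's own figure.** Sample Size states 300 drivers, 90% power, alpha 0.05, a difference of at least 20 points and 10% loss. The least favourable pair, 40% vs 60%, needs 130 per arm; 130/0.9 = 145 per arm, or 290. Power at 135 per arm is 91.2%. The plan's figure is reproduced, with site playing no part in it.

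**Assumptions.** Three equal sites, 1:1 within site, two-sided 5%. The site rates of DCS<25 are assumed, since the documents give none.

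**Aim 1a type I error with site ignored.** The arm-only test uses variance 0.25 per driver (overall rate 50%). Under within-site balance the true value is V = mean of p(1−p) over sites. Type I error = 2(1 − Φ(1.96·√(0.25/V))).
- 40/50/60%: V = (0.24+0.25+0.24)/3 = 0.2433, ratio 1.027, type I 4.7%
- 30/50/70%: V = (0.21+0.25+0.21)/3 = 0.2233, ratio 1.119, type I 3.8%
- 20/50/80%: V = (0.16+0.25+0.16)/3 = 0.19, ratio 1.316, type I 2.5%

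**Aim 1a power.** A common odds ratio is solved to give an average 20-point difference. Example, 30/50/70%, n=300:
- Ignored: (0.2 − 1.96×0.0577)/0.0536 = 1.62, power 94.7%.
- Site-stratified score test: (15.0 − 1.96×4.113)/4.020 = 1.73, power 95.8%.

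| Site rates | n=300, ignored / fitted | Loss | n=270, ignored / fitted | Loss |
|---|---|---|---|---|
| 40/50/60% | 94.0 / 94.3% | 0.3 | 91.5 / 91.9% | 0.4 |
| 30/50/70% | 94.7 / 95.8% | 1.0 | 92.3 / 93.8% | 1.4 |
| 20/50/80% | 96.0 / 97.8% | 1.8 | 93.9 / 96.5% | 2.6 |

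Losses are taken before rounding. Simulated logistic Wald tests lose up to 3.5 points at n=270 and the widest spread, partly because an arm-only test with exactly equal arms is discrete. If a measured covariate in both models carries half the site effect, the loss at the two wider spreads is about half a point.

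**Chance that site is dropped.** Take Table 3's seven example demographics as independent tests with 100 drivers per site:
- No true differences: 0.95^7 = 70%.
- One variable at 45/50/55% (chance of non-significance 0.774): 0.774×0.95^6 = 57%.
- Three variables at 40/50/60% (0.282 each): 0.282^3×0.95^4 = 2%.

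The expected Aim 1a loss at the widest spread therefore runs from 0.018×1.8 = 0.03 to 0.698×1.8 = 1.3 points at n=300, and up to 0.698×2.6 = 1.8 at n=270.

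**Aim 2 interaction.** Simulation: n=300, a 30% subgroup unrelated to site, 30 points in one group and 0 in the other. Type I error is about 5% with or without site. Power, ignored vs fitted, is 67.2 vs 68.3%, 67.7 vs 71.7% and 67.5 vs 78.2%. To compare efficiency, convert to expected z:
- Aim 2 at 30/50/70%: (0.459+1.96)/(0.574+1.96) = 0.955. Across the three spreads: 0.987, 0.955, 0.881.
- Aim 1a at 30/50/70%: (0.2/0.0577)/(15.0/4.113) = 0.950. Across the three spreads: 0.988, 0.950, 0.884.

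The proportional loss is the same. More points are lost in Aim 2 because its power is near 67% rather than 95%. If the demographic check governs Aim 2, the 4.0-point loss is weighted to between 0.018×4.0 = 0.07 and 0.698×4.0 = 2.8 points, and the 10.7-point loss to between 0.2 and 7.5.

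**Aim 1b (continuous, two-sided).** If site explains 2%, 5% or 10% of variance, type I error is 2(1 − Φ(1.96/√(1−R²))) = 4.8%, 4.4% or 3.9%. Power of 80% falls to Φ(1.96+0.84−1.96/√(1−R²)) = 79.4%, 78.5% or 76.9%.

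**The case against.** The strongest reply is that this hardly matters. The error is conservative, the loss is a point or two under assumed rates, and the rule may seldom drop site: the plan says "we plan to include clinics associated with three sites to provide geographic diversity, along with access to populations with racial and ethnic variability", so some demographic test will probably be significant. The large losses need sites that look alike demographically yet differ by 40 to 60 points in DCS<25. All of this stands and keeps the point minor. It does not justify the rule, because fitting site costs almost nothing (simulated interaction power with no site effect: 67.5% without site, 67.3% with it).

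A reader might infer four stronger things, none of which the documents support:
- **That the error is worse for Aim 2.** Interaction type I error is nominal either way and the efficiency loss is proportionally equal. Nor is site clearly excluded there, since Analysis for Aim 2 repeats the site check before calling the test unadjusted.
- **That the rule lets the analyst pick a model by its result.** The trigger is written down and uses baseline data only.
- **That the two branches must report different effect measures.** The site-ignored branch refers to the tests set out later, and the Aim 1a paragraph specifies logistic regression regardless of the site check.
- **That the events proviso can simply be deleted.** With 20-50% below 25, 270 drivers give 54 to 135 events, or 18 to 45 per parameter for arm plus site. Adding seven demographics at one parameter each makes 10 parameters, with 5.4 to 13.5 each. The pilot DCS means quoted under Aim 1a (22.5 falling to 7.5) are both below 25; if 90% scored below 25, only 27 non-events would remain.

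**Conclusion.** The point holds as a low-priority improvement. Site is the stratum, its inclusion turns on the wrong evidence, and when it is dropped and prognostic the Aim 1a test is slightly conservative, with a loss of 0.3 to 1.8 points at n=300 and 0.4 to 2.6 at n=270. These sizes rest on assumed site rates, equal sites and a 20-point effect, and apply only if every demographic test is non-significant. The primary conclusion is not threatened. For Aim 2 the defect is ambiguity about whether site may enter, plus the same proportional loss if it does not.

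A site main effect should not be expected to cure an effect of the decision aid that itself varies by site. In one simulated case of that kind, with subgroup prevalence also differing by site, interaction type I error was 11.4% with site ignored and 11.7% with it fitted.

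**What to change.** 1. In Analysis for Aim 1, replace the demographic trigger: site is a pre-specified fixed effect (2 degrees of freedom) in the Aim 1a model and in the Aim 1b and 1c models, whatever the across-site comparison shows. Keep that comparison as a descriptive table.
2. In Analysis for Aim 2, state that site is a main effect in the interaction models and that unadjusted means no other covariates.
3. Keep the events proviso but define it. If the rarer DCS category, or the rarer category of a binary secondary outcome, is too small for the parameters in the model (for example under 10 per parameter, an assumed convention), use a site-stratified Mantel-Haenszel comparison, at each time point for longitudinal outcomes, instead of dropping site.
4. If the Aim 1a switch to comparing means is used, keep site in that model too.
5. Report a site-standardised difference in the proportion with DCS<25 beside the odds ratio, which becomes conditional on site.

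The cost is SAP wording and two parameters. N is unchanged.

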Longitudinal outcomes: Key longitudinal outcomes, linked to our theoretical framework (Figure 1), are psychosocial and mobility-related.

-Depression: We will measure depression using the PROMIS 4-item scale, with higher scores indicating higher depression. All PROMIS scores are analyzed as standardized T-scores (mean=50, SD=10).

-Decision regret: The Ottawa Decision Regret Scale. This validated measure correlates with decision satisfaction and conflict, and overall quality of life. Scored from 0-100, high scores represent higher regret.

-Life space: Life space is a global measure of mobility and community engagement. The Life-Space Assessment instrument (UAB Study of Aging) is a validated tool assessing recent mobility and function. Composite scores range from 0 (bedbound) to 120 (travel out of town

AUTO Study Protocol: Version Date: 12/22/21 PI: [name], MPH COMIRB No: 19-0059 every day without assistance); scores of  $\leq$ 60 are correlated with lower levels of social participation and higher mortality.

-Driving behaviors: We will assess driving frequency (days per week), avoidance in certain situations (e.g., night), driving cessation (none, partial, complete), and self-reported crashes (≥1 versus none).

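### Aim 1b has conflicting analyses: logistic GEE in the general text, linear models in its own paragraph, and a depression cut in Table 3 at the scale's reference mean

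*Combined protocol and SAP*

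**What the plan says.** All references are to the combined protocol and SAP, under Outcome Measures and Analysis.

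- **Analysis for Aim 1 (general text).** If sites do not differ significantly, "we will ignore site and formally test the differences in proportions or means as described below". If they do, and the number of events allows, "we will use separate bivariate logistic regression models for each aim described below, with a fixed effect for site and with treatment arm"; arm is the predictor of interest. A separate sentence follows: "For longitudinal analyses, we will conduct logistic regression with unstructured correlation of generalized estimating equations (GEE"), to handle repeated observations. It carries no site condition and is not restricted to binary outcomes.
- **Aim 1b.** The hypothesis is "reduced prevalence of depressive symptoms and of decision regret but maintained life space" at 12 and 24 months. The paragraph first announces descriptive summaries (proportions with confidence intervals, or medians with interquartile ranges). Then, for each outcome: "We will utilize GEE with a linear link, and a linear mixed model (LMM) with a random intercept, fixed effects and a linear link".
- **Aim 1c (driving behaviours).** "We will apply GEE with a logistic link, and a generalized LMM (GLMM) with a random intercept and a logistic link for each outcome".
- **Secondary analyses after Aim 1c.** The gender analyses of Aims 1a to 1c are assigned to logistic regression and GLMM.
- **Table 3.** Depression is scored for hypothesis 1b as a T-score above 50, but as continuous where it is a covariate for 1c. Decision regret and life space are scored for 1b as "Descriptive (contin", that is, continuous.
- **Longitudinal outcomes.** "All PROMIS scores are analyzed as standardized T-scores (mean=50, SD=10"). Regret runs from 0 to 100 with no threshold. Life space runs from 0 to 120; a score of 60 or less is mentioned as a correlate of poorer outcomes, but no analysis uses it.

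**The concern.** Aim 1b is a named hypothesis about psychosocial effects, yet an analyst following the plan could fit either of two model families to depression and comply with the text both ways. One yields a difference in mean T-score. The other yields an odds ratio for being above 50. These answer different questions and have different power, and the choice could be made after the data are seen.

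The binary version also carries a misleading label. By the plan's own definition of the T-score, above 50 means above the reference mean, so calling that proportion a prevalence of depressive symptoms would overstate what was measured. For regret, the hypothesis uses prevalence language but nothing defines who counts as having regret.

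**Working it through.** **1. The plan's own figure.** The Sample Size section gives 300 drivers (150 per arm), a difference of at least 20 points in the proportion with DCS below 25, 90% power, alpha 0.05 and 10% loss. Evaluable per arm: 150 × 0.90 = 135. The hardest 20-point case is 40% against 60%:

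- standard error under the null: √(2 × 0.5 × 0.5 / 135) = 0.0609
- standard error under the alternative: √((0.4 × 0.6 + 0.6 × 0.4) / 135) = 0.0596
- power = Φ((0.20 − 1.96 × 0.0609) / 0.0596) = 91.2%

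The stated size is supported for the primary outcome. The plan gives no effect size or power for Aim 1b.

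**2. Outcome by outcome for Aim 1b.**

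| Outcome | General longitudinal text | Aim 1b model | Hypothesis 1b | Table 3 scoring |
|---|---|---|---|---|
| Depression | logistic GEE | linear GEE and LMM | prevalence | cut at T>50 |
| Decision regret | logistic GEE | linear GEE and LMM | prevalence | continuous |
| Life space | logistic GEE | linear GEE and LMM | maintained | continuous |

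The model conflict covers all three outcomes. The Table 3 conflict concerns depression alone. For regret, the hypothesis wording disagrees with both the model and the table. For life space, only the general sentence is out of line.

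**3. What T>50 means.** With mean 50 and SD 10, P(T>50) = 1 − Φ((50 − 50)/10) = 0.500 in a normal (symmetric) reference population. The trial sample's mean is not stated. Assuming SD 10, a sample mean of 46 gives 1 − Φ(0.4) = 34.5%, and a mean of 52 gives 57.9%.

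**4. Power for depression, as illustration.** Effects are assumed. Settings: 135 per arm, two-sided 0.05, normal T-scores, one time point, no baseline adjustment.

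For means, power = Φ(d√(135/2) − 1.96):
- d = 0.35: Φ(2.876 − 1.96) = 82.0%
- d = 0.30: Φ(2.465 − 1.96) = 69.3%

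For a split at the overall mean, the proportions are Φ(±d/2):
- d = 0.35: 56.95% against 43.05%, power 62.8%
- d = 0.30: 55.96% against 44.04%, power 50.0%

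With the cut fixed at T=50 and an assumed control mean of 46 or 50:

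| Mean shift | Continuous T-score | T>50 (control mean 46 to 50) |
|---|---|---|
| 3 points | 69% | 46% to 50% |
| 4 points | 91% | 68% to 74% |
| 5 points | 98% | 85% to 90% |

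The general text also states a one-sided 0.05 level next to its two-sided default, which is a separate inconsistency. At one-sided 0.05, the 3-point shift from a control mean of 50 gives 79% against 62%, so the loss does not depend on sidedness.

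**The case against.** The strongest reply is that specific text governs general text: the Aim 1b paragraph names a linear model for each outcome, and the general logistic sentence was written with binary outcomes in mind. T>50 sits in a column about scoring, not modelling, and the Aim 1b paragraph allows descriptive proportions, so a reported percentage above 50 beside a linear model would be coherent. This is a reasonable guess at the intent, but the plan does not say it. The hypothesis is still framed as prevalence. Table 3 treats the same measure as continuous for 1c, so the cut for 1b looks deliberate. The gender analyses also point Aim 1b back towards logistic regression, although a GLMM with an identity link would be a linear model.

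Three stronger readings are tempting and are not supported:

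- **That the site comparison decides the Aim 1b model.** The bivariate logistic sentence depends on site differences and on enough events, wording that suits binary outcomes, and a bivariate logistic model is what Aim 1a plans for drivers and family members jointly. The alternative branch allows proportions or means. Neither the longitudinal GEE sentence nor the Aim 1b model carries a site condition. The number of demographic tests is not stated either, so no chance of triggering that branch can be given.
- **That Table 3 imposes cuts on all three outcomes, or wrongly omits them.** Its continuous scoring of regret and life space agrees with the Aim 1b model. A continuous outcome needs no cut.
- **That a person of average mood is labelled as having symptoms.** A T-score of exactly 50 is not above 50. The statement holds for a population, about half of which lies above its own mean.

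**Conclusion.** The concern holds for the secondary Aim 1b outcomes. The general longitudinal sentence and the Aim 1b paragraph prescribe different model families. For depression and regret, the prevalence wording keeps the ambiguity alive even if the specific text is taken to govern. The depression cut equals the reference mean, and regret has no definition of prevalence.

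For depression the choice matters: about 19 percentage points of power at either assumed effect (82% against 63%, and 69% against 50%). These figures rest on assumed effect sizes, normal scores and a single unadjusted time point. The planned repeated measures and covariate adjustment would change the levels, so they illustrate the cost of dichotomising and do not predict the trial's power.

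The primary analysis of DCS below 25 and the sample size of 300 are unaffected. This should be corrected before outcome data are analysed, but it does not threaten the main result.

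**What to change.** 1. In the general Aim 1 text, and in the gender analyses, limit logistic models to binary outcomes: DCS below 25, and driving reduction or cessation.
2. State that the PROMIS T-score, decision regret (0 to 100) and life space (0 to 120) are analysed with the linear model already given under Aim 1b.
3. Reword Hypothesis 1b so that depression and regret refer to mean scores rather than prevalence.
4. In Table 3, remove T>50 as the 1b scoring rule, or keep it as a descriptive summary labelled as above the reference mean.

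The cost is wording in the analysis text, the hypothesis and one table cell, with no new data or added sample. The drawback is that the depression result is stated as a mean difference, which some readers find harder to interpret than a percentage.
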